6.4 Efficacy Assessments

6.4.1 Best Overall Response (BOR) based on GRS

The best overall response (BOR) based on the GRS according to Olsen (2011)¹ criteria is described as follows.

Tumor assessment and response criteria will be according ISCL/EORTC response criteria described in Olsen (2011)¹ criteria. This is a composite measure of tumor burden in skin, lymph node, blood, and viscera. The documented date of CR/PR/SD/PD for GRS will be based on the corresponding mSWAT score assessment date (implemented for IRC assessment by IRC and derived programmatically for Investigator assessment). Assessments showing non-PD after a single PD, or assessments showing non-PD after two consecutive PD evaluations within 7 days of each other, will be included in the determination of BOR. The key points of BOR derivation are described as follows.

- **Complete Response (CR).** BOR of CR can be achieved by the following situations:
 - BOR is CR when the duration between the two CRs is ≥ 3 weeks for two consecutive CRs or two CRs with “unknown” or “missing” assessments in between.

The documented start date of CR is defined as the date of mSWAT score assessment date corresponding to the initial CR.

- **Partial Response (PR).** When BOR of CR is not achieved, BOR of PR can be achieved by one of the following situations:
 - BOR is PR when the duration between the two responses (PR or CR) is ≥ 3 weeks for two consecutive PRs, the order of CR, PR, or the order of PR, CR, without intervening of SD/UNK or missing assessments.
 - BOR is PR when the duration between the two responses (PR or CR) is ≥ 3 weeks for two PRs, or the order of PR, CR, with up to two intervening SD assessments in between.
 - BOR is PR when the duration between the two responses (PR or CR) is ≥ 3 weeks for two PRs, the order of CR, PR, or the order of PR, CR, with “unknown” or “missing” assessments in between.

The documented start date of PR is the date of mSWAT score assessment date corresponding to the initial PR or CR

- **Stable Disease (SD).** When BOR of CR/PR is not achieved, BOR of SD can be achieved by the following:
 - If subject at least once had an overall timepoint evaluation of CR/PR/SD that was recorded ≥ 3 weeks after the first dose of study drug.

- **Progressive Disease (PD).** When BOR of CR/PR/SD is not achieved, if subject at least once had an overall time point evaluation of PD, then the BOR is PD.

The date of documented PD is:

- If subject is not treated beyond the initial PD, date of PD should be used.
- If subject is treated beyond the initial PD (per protocol), date of the initial PD should be used if consecutive PDs; if there are intervening SD/PR/CR between the two PDs, date of the later PD should be used.
- **Unknown (UNK).**
 - No baseline assessment
 - No post-baseline evaluations GRS assessment
 - Early SD (SD <21 days from first dose date)
 - Subject has only UNK (assessment not possible) for Global Response Score for all postbaseline Tumor Timepoint Response Assessment.

More details regarding BOR derivation can be found in the Analysis Data Model (ADaM) Data Specification document.

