### Efficacy Assessments:

The ISCL/EORTC response criteria for mycosis fungoides and Sezary syndrome (Olsen 2011) will be used for efficacy analysis in the Lead-In as well as for primary efficacy analysis in the Main Study.

Tumor responses will be assessed by an independent central Response Review Committee (IRC) (Imaging Core Laboratory) for primary efficacy analysis in the Main Study. Tumor responses will also be assessed by the site investigator, and these site assessments will be used to make subject treatment decisions.

The response criteria described in Prince (2010) will be used as a supplemental alternate method (SAM) for the secondary objective of ORR. This supplemental assessment will be conducted by the IRC only.

For both the Lead-In and Main Study, photographs and CT scans will be sent by the investigator site to an Independent Imaging Core Laboratory designated by the sponsor for analysis. Laboratory results, including blood, as well as investigator skin assessments as entered in the CRF, will be sent to the Core Laboratory by the sponsor. At the time of data cutoff for primary analysis of the Main Study, the sponsor may choose to discontinue sending data (including photographs and scans) to the Imaging Core Laboratory.

Tumor assessment schedule (see protocol body for details):

- At screening, skin, lymph node assessment by palpation, blood assessment, and CT scan for assessment of nodal and visceral disease.
- During treatment: (1) skin and blood disease assessment, on Day 1 of every cycle, (2) lymph node assessment by palpation and CT scans of nodal disease (as needed) and visceral disease (as needed), and (3) lymph node biopsy is only recommended in situations where the histology would affect the Global

Response score. End-of-treatment tumor assessments should be performed if required for Global Response Score determination.

Follow-up: (1) skin and blood disease assessment to be performed every 4 weeks for 1 year after end of study treatment, then every 12 weeks thereafter for up to 3 years, or sooner if clinically indicated, (2) other assessments e.g. lymph node palpation, CT scans of nodal and visceral disease, or lymph node biopsy only if appropriate, as described in [Section 9.5.2.2](#) of the protocol.

Measurement of Tumor Burden (see protocol body for details)

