**Secondary Efficacy Variables:**

- Duration of response (DOR) is defined as time from the date when criteria for response (CR or PR) based on GRS was first met until the date when the response was first lost (date of loss is date when first meets criteria for PD).
- Time to response (TTR) is defined as time from the date of first dosing to the date when criteria for response (CR or PR) based on GRS are first met.

- Skin response based on the mSWAT score is defined as the proportion of subjects with best response of CR or PR in skin.
- Duration of skin response based on the mSWAT Score is defined as time from the date when criteria for response in skin (CR or PR) was first met until the date when the response was first lost (date of loss is date when first meets criteria for global response PD).
- Time to skin response based on the mSWAT Score is defined as time from the date of first dosing to the date when criteria for response in skin (CR or PR) are first met.
- Objective response as determined by the alternate criteria of [Prince \(2010\)](#)

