#### **1. Skin Disease Assessment**

Skin tumor burden will be quantified using a modified Severity Weighted Assessment Tool (mSWAT) that provides an mSWAT score. The mSWAT score measures the body surface area (BSA) involved in skin disease with a weighting factor applied according to the severity of the type of skin lesion, which can be patch, plaque, or tumor. The mSWAT

can be utilized to track erythroderma by the summation of BSA involved with patch disease (macular erythema) and plaque disease (erythema with induration/edema). In addition, subject(s) should be evaluated for the appearance of new skin tumor lesion(s) at each time point after the initiation of treatment. A sample of the worksheet for calculating the mSWAT score is provided in [Appendix 4](#). Note: The worksheet for use at the site will be provided separately to each site.

*Supplemental Assessment Method (SAM) using Prince (2010) Criteria (only for subjects with skin lesions comprising < 10% of BSA)*

Since the IRC will perform a secondary analysis based upon the method of [Prince \(2010\)](#), a supplemental measurement will be made by the site investigator at the time of mSWAT assessment, for subjects with skin lesions comprising < 10% of BSA. The investigator will identify, photograph, and measure up to five representative skin lesions (generally the largest and most representative of different locations, such as chest, abdomen, leg, arm, head, neck, if applicable; measurements will be of two-dimensional perpendicular diameters). These measurements will be collected on the eCRF and will be used only by the IRC. These lesions (even if they have disappeared) should be evaluated and photographed at all mSWAT assessment time points. A sample of the worksheet for collecting skin lesion data per supplemental assessment method (by Prince 2010) is shown in [Appendix 4](#). Note: The worksheet for use at the site will be provided separately to each site.

The assessment schedule is as follows:

- a. At Screening, assessment to determine study eligibility
- b. During treatment
  - Day 1 (-3 days) of every treatment cycle (minus 3-day window allowed)
- c. At EOT, if required for Global Response Score determination
- d. During Follow-up: every 4 weeks ( $\pm$  1 week) for 1 year after end of study treatment, then every 12 weeks ( $\pm$  3 weeks) thereafter for up to 3 years, or sooner if clinically indicated

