**Main Study**

To be performed as necessary for monitoring of lymph node disease, with frequency according to the judgment of the investigator.

ii. CT Scan

CT assessment if any of the following conditions are met, during Treatment or Follow-up **in Lead-in part**

- In subjects with more advanced disease (maximum/current TNMB greater than T1-2N0M0B0-1) at study entry, the CT assessment is to be performed at the time of CR or PR in skin disease
- In subjects with early disease (maximum/current T1-2N0M0B0-1) at study entry, the CT is to be performed at time of CR or PR in skin disease, only if this affects the GRS
- In all subjects, the CT is to be performed any time there is suggestion of new or progressive disease/relapse in lymph nodes or viscera (by

palpation of lymph nodes, liver, and/or spleen) and only in the absence of PD by skin or blood

- Exceptions: the CT need not be performed under the above circumstances if the lymph node response is not needed for GRS, e.g., if CR or PR is in skin but PD is in blood.

CT assessment **in Main Study** is as described in [Appendix 5 Figure 1](#).

- In subjects with N0 and N1 at study entry:
  - CT is to be performed at time of CR or PR in skin disease, only if this affects the GRS
  - CT is to be performed any time there is suggestion of new or progressive disease/relapse in lymph nodes or viscera (by palpation of lymph nodes, liver, and/or spleen) and only in the absence of PD by skin or blood
- In subjects with N2, N3 and Nx at study entry:
  - CT scans of the affected/suspected area are required every 3 cycles beginning at Cycle 3 (±1 week)
- Exceptions: the CT need not be performed under the above circumstances if the lymph node response is not needed for GRS, e.g., if there is already a PD assessment in another disease site.

- iii. Lymph node biopsy: A repeat peripheral lymph node biopsy during the study is recommended only in situations where the histology would affect the Global Response score. A fine needle aspirate or core biopsy with supportive ancillary studies may be acceptable.

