### 3. Blood Disease Assessment

Blood tumor burden will be assessed by quantifying CD4+CD26 cells by flow cytometry; CD4+CD7 cells may be used in CD26+ subjects.

Assessment frequency

- a. At Screening
- b. During treatment
  - i. Day 1 (-3 days) of every treatment cycle
- c. At EOT, if required for Global Response Score determination
- d. During Follow-up: Every 4 weeks (± 1 week) for 1 year after end of study treatment, then every 12 weeks (± 3 weeks) thereafter for up to 3 years, or sooner if clinically indicated.

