**Appendix 4 Table 5 Definition of the Global Response Score**

Global Score	Definition	Skin	Nodes/Blood/Viscera
CR	Complete disappearance of all clinical evidence of disease	CR	All categories have CR/NI
PR	Regression of measurable disease	CR PR	All categories do not have a CR/NI and no category has a PD No category has a PD and if any category involved at baseline, at least one has a CR or PR
SD	Failure to attain CR, PR, or PD representative of all disease	PR SD	No category has a PD and if any category involved at baseline, no CR or PR in any CR/NI, PR, SD in any category and no category has a PD
PD	Progressive disease	PD in any category	
Relapse	Recurrence disease in prior CR	Relapse in any category	

CR = complete response, PD = progressive disease, NI = noninvolved, PR = partial response, SD = stable disease  
Notes:

1. No Global Score of CR can be assigned if the subject received concomitant therapy of topical steroids or low dose systemic steroids; in such a case, the maximum response is PR.
2. In cases where the definition of PD or relapse is met but the clinical impression is questionable, the PD should be confirmed after at least 4 weeks in order to avoid premature removal of the subject from the study.
3. Only N3 is considered as nodal disease (nodal involvement) for Global Response Score assessment.

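### SAP 6.4.1 dates global PD by an undefined corresponding mSWAT visit, so PD found by off-schedule CT or biopsy is not dated when the protocol's PD criteria are first met

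*SAP*

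**What the plan says.** SAP 6.4.1 has one dating rule for all global scores: "The documented date of CR/PR/SD/PD for GRS will be based on the corresponding mSWAT score assessment date". The IRC applies it to its own data, and investigator dates are derived by program. CT, blood and biopsy findings have no exception. The word *corresponding* is not defined: it could mean the same, nearest, previous or next skin visit. The later bullets on the PD date only choose between successive PDs when treatment continues; they do not change the anchor.

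SAP Table 2 (section 6.5.3.1), row 2, covers progression between scheduled visits. It uses the PD date of the GRS assessment, which 6.4.1 sends back to the mSWAT date.

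The protocol differs. Appendix 4 Table 5 defines global PD as "PD in any category". The Synopsis ends DOR as follows: "date of loss is date when first meets criteria for PD". PFS and TTP also run to the first date on which PD criteria are met, and duration of skin response ends on global PD. For Main Study subjects who enter as N0 or N1, section 9.5.2.2 says "CT is to be performed any time there is suggestion of new or progressive disease/relapse in lymph nodes or viscera", provided skin and blood do not already show PD.

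SAP 8.1 does not list mSWAT dating as a change from the protocol. It points to the revision history, which presents the date-of-response rule as a clarification.

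**The concern.** A triggered CT has no fixed day, and it is done only when skin and blood are not progressing. If it shows PD, the protocol's event date is the day the criterion was met. The SAP moves that event to a skin visit, which may be earlier or later and may itself have been scored SD or PR. Because *corresponding* is open, the IRC and the investigator-data program could also date the same progression differently.

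The endpoints at stake are DOR and duration of skin response (secondary) and PFS and TTP (exploratory). DOR deserves care because, in a single-arm study, it is read alongside the response rate.

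**Working it through.** **1. The plan's own figures.** The documents state no size for a dating error. The nearest stated figures are the missed-visit limits under SAP Table 2, and they reproduce exactly:
- on treatment: 3×2×7 + 3 − 1 = 44 days
- follow-up year 1: (4+1)×2×7 − 1 = 69 days
- after year 1: (12+3)×2×7 − 1 = 209 days

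These limits span two visit intervals. The dating offset depends on one interval.

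**2. Inputs.**
- mSWAT on treatment (protocol 9.5.2.2, skin): "Day 1 (-3 days) of every treatment cycle (minus 3-day window allowed", in 21-day cycles.
- Blood on treatment (9.5.2.2, blood): "Day 1 (-3 days) of every treatment cycle".
- Follow-up (Synopsis): "skin and blood disease assessment to be performed every 4 weeks for 1 year after end of study treatment, then every 12 weeks thereafter". Section 9.5.2.2 adds windows of ±1 week and ±3 weeks.
- Scheduled CT for N2, N3 and Nx (9.5.2.2): every 3 cycles, ±1 week.
- Longest permitted cycle delay, for scheduling (9.4.1.5): 42 days.

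**3. Largest offset between a non-skin PD and an mSWAT date.**
- Blood on treatment: both lie in the window −3 to 0, so 0–3 days. In follow-up I assume skin and blood are done at the same visit, as the Synopsis pairs them.
- Scheduled on-treatment CT: the scan lies in −7 to +7 and mSWAT in −3 to 0. CT minus mSWAT therefore runs from −7 − 0 = −7 to 7 + 3 = +10 days.
- Off-schedule CT or biopsy: the bound is the longest permitted mSWAT interval if the previous or next visit is used, and half of it if the nearest is used. Follow-up windows apply at both ends of the interval.

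| Period | Longest interval (adjacent visit) | Nearest visit |
|---|---|---|
| On treatment, no delay | 21 + 3 = 24 days | 12 days |
| On treatment, 42-day delay | 21 + 42 + 3 = 66 days | 33 days |
| Follow-up year 1 | 28 + 7 + 7 = 42 days | 21 days |
| After year 1 | 84 + 21 + 21 = 126 days (126/30.4375 = 4.1 months) | 63 days |

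Table 4 footnote j also lets a cycle start one day early or late from Cycle 3. That could add at most two days to the on-treatment intervals and is left out.

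Skin PD is already dated by mSWAT, and SAP Table 2 rows 5 and 6 date deaths by date of death. Neither moves.

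**4. Effect on median DOR.** This is a simulation of 400,000 responders. None of the following comes from the documents: exponential DOR, median 6 or 12 months, 5%, 10% or 30% of PDs seen only on off-schedule CT, and scan timing independent of visits. Skin visits fell every 21 days to day 168, then every 28 days for 13 visits, then every 84 days.

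| Median | CT-only share | Shift in days: previous / nearest / next visit |
|---|---|---|
| 6 months | 5% | −0.7 / 0.0 / +0.9 |
| 6 months | 10% | −1.4 / +0.1 / +1.6 |
| 6 months | 30% | −5.6 / +0.2 / +6.5 |
| 12 months | 5% | −1.2 / −0.6 / +0.1 |
| 12 months | 10% | −2.0 / −1.3 / +0.2 |
| 12 months | 30% | −1.2 / −1.2 / +0.5 |

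Among the off-schedule CT-only PDs, 46–58% lay a week or more from the nearest mSWAT. None was 60 days or more away with nearest-visit dating; about 3–10% were with previous-visit dating.

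**5. How many events.** Only N3 counts as nodal disease for the global score (Appendix 4 Table 5, note 3), and a new node must be histologically N3 to be PD (Appendix 4 Table 3). Main Study subjects with visceral disease at entry are excluded. In the Stage I–III set, CT-only PD is therefore mainly a new biopsy-proven N3 node or new visceral disease. The documents give no count.

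**The case against.** A composite score needs one date per timepoint, and the skin visit is a natural anchor. The IRC works under a Tumor Assessment Charter (protocol 9.7.1.7), and SAP 6.4.1 refers to an ADaM specification. Neither is available here, and either may define *corresponding*. Skin may also be assessed "or sooner if clinically indicated", so an off-schedule scan can have an mSWAT close to it. Suspicion may arise from palpation at a skin visit, and assessment may continue after a first PD. The endpoints are secondary or exploratory, and the simulated shift is small.

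Most of this stands, and it limits the size of the point. It does not remove it. An extra mSWAT is permitted but not required, and Main Study palpation frequency is left to the investigator. A definition in another document would settle the ambiguity, but PD would still not be dated when its criterion is met, and SAP 8.1 would still be silent.

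It is tempting to go further and move CR/PR to the last component needed, using that date for the 3-week confirmation too. That could change the primary endpoint. Take skin PR at Cycle 3 Day 1, the deciding CT 5 days later, and PR again at Cycle 4 Day 1: the interval falls from 21 days to 21 − 5 = 16, and the pair no longer confirms.

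**Conclusion.** The point holds for a narrow class of events. For PD found by off-schedule CT or biopsy, the SAP rule as written departs from the protocol's event date, leaves the replacement date undefined and is not listed in SAP 8.1. The per-event bounds are those in the table; the effect on median DOR is likely to be small, at most 6.5 days in the scenarios run. That last figure rests on the assumed medians and CT-only shares. The statement that few Stage I–III events are affected rests on the N3 and visceral criteria, not on a count.

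Two stronger readings are not supported:
- A reader might infer that every non-skin progression is misdated by a week to several months. Blood follows the skin schedule and scheduled on-treatment CT stays within 10 days. An offset above two months needs an off-schedule finding after follow-up year 1 or during a long cycle delay, with no added mSWAT and, apart from the extreme 63-day case, previous- or next-visit dating.
- A reader might infer that back-dated PD could cancel a confirmed response and so change ORR. SAP 6.4.1 assigns dates, not timepoint scores. Best response rests on two qualifying scores at least 3 weeks apart, and non-PD scores after a single PD still count.

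**What to change.** - **PD date.** In SAP 6.4.1, for DOR, PFS, TTP and duration of skin response where it ends on global PD, date PD by the earliest component assessment (CT, blood, biopsy or mSWAT) that meets PD criteria. Point Table 2 row 2 to that date. Use the same rule for IRC and investigator data, and say whether a new node is dated by the scan or by the biopsy that proves N3.
- **Response date.** Keep mSWAT as the anchor for CR/PR and for the 3-week confirmation interval, so the primary ORR derivation is unchanged. Define *corresponding* with a maximum window, for example ±7 days.
- **Sensitivity analysis.** Report TTR and DOR with response dated by the last component needed, as a sensitivity analysis only.
- **Disclosure.** List the mSWAT dating convention in SAP 8.1.

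The cost is minor reprogramming and aligning the IRC's dating instruction. No new assessments are needed.

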## 7.4 CTCL and Current Therapeutic Options

Cutaneous T-cell lymphomas account for about 10 to 15 percent of all cases of non-Hodgkins lymphoma. The most common variant of CTCL (about 50% of cases) is mycosis fungoides (MF). Less common is Sézary syndrome (SS), a leukemic variant that affects about 5% of patients with CTCL.

Typically, the natural history of MF is indolent, with cutaneous symptoms waxing and waning over a period of years. Cutaneous disease progresses from an eczematous patch/plaque stage (T1) to plaque stage covering (T2), and finally to tumors (T3) that frequently undergo necrotic

ulceration. SS is thought to be an advanced form of MF with generalized erythroderma (T4) and peripheral blood involvement at presentation. The prognosis of patients with MF/SS is based on the extent of disease at presentation; patients with stage IA disease have a median survival of 20 or more years while patients with stage III through stage IV disease have a median survival of less than 5 years.

A number of therapeutic options are available to treat CTCL; these include skin-directed therapies, phototherapies, radiation, and systemic therapies. Often a combination of either sequential or concomitant therapies gives a higher rate of response, but patients with advanced disease often relapse and no therapy has been proven to be curative. Extensive skin or blood involvement, tumors, or nodal disease require systemic therapy with biologic response modifiers, bexarotene, ONTAK (denileukin diftitox), skin radiation, and single- or multi-agent chemotherapy. Over the past few years, the FDA has approved two histone deacetylase inhibitors (HDIs), vorinostat and romidepsin, for treatment of CTCL.

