## 6. Best Response (Objective Response)

The Best Response or Objective Response for the subject is the best Global Response Score that is at least 3 weeks in duration.

Please note the following:

- [Olsen \(2011\)](#) states 4 weeks duration, but this was based on drugs that had 4-week treatment cycles. The intent is that the response should last at least one treatment cycle (based on consult with study investigators who are also co-authors of Olsen (2011)).

- Treatment may continue after first assessment of disease progression (PD) if the investigator is of the opinion that PD needs to be confirmed (see [Section 9.4.1](#)). If PD is not confirmed and subject continues treatment, any subsequent time point assessment of CR/PR will be used in assessing Best Response.

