6.4.2 Best Overall Response (BOR) for Skin Response

BOR for skin response will follow the same approach as described in [section 6.4.1](#) based on timepoint skin response instead of GRS assessment.

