6.5.1 Primary Efficacy Analysis

The primary endpoint is the ORR based on Olsen (2011)¹ criteria, using response assessment data by IRC. The ORR is the proportion of subjects achieving a BOR of confirmed CR or PR. The Primary Efficacy Analysis Set will be used for analysis.

The 2-sided, exact 95% CI of ORR will be calculated using the Clopper-Pearson method. The treatment will be considered efficacious and demonstrating the clinical benefit of E7777 if the lower bound of the 2-sided 95% exact CI of the observed ORR exceeds 25%.

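### The primary response rate counts a PR interrupted by up to two assessed SD visits as confirmed, which the SAP does not reconcile with the protocol's requirement that the response last at least 3 weeks

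*SAP*

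**What the plan says.** Protocol Appendix 4, section 6 defines the endpoint: "The Best Response or Objective Response for the subject is the best Global Response Score that is at least 3 weeks in duration". It explains that the 3 weeks replace the 4 weeks of the published criteria because cycles here are 21 days: "The intent is that the response should last at least one treatment cycle".

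SAP 6.4.1 turns this into derivation rules. A PR is confirmed by two consecutive responses at least 3 weeks apart. A separate bullet lets unknown or missing assessments fall between the two responses. A further bullet confirms a PR "for two PRs, or the order of PR, CR, with up to two intervening SD assessments in between", again with at least 3 weeks between the two responses. The start of response is dated from the initial PR or CR.

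SAP 6.5.1 builds the primary analysis on this: "The ORR is the proportion of subjects achieving a BOR of confirmed CR or PR". Efficacy is declared "if the lower bound of the 2-sided 95% exact CI of the observed ORR exceeds 25" per cent. SAP 6.4.2 extends the derivation to skin: "BOR for skin response will follow the same approach".

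Skin disease is assessed on "Day 1 (-3 days) of every treatment cycle (minus 3-day window allowed") (Protocol 9.5.2.2), and blood on the same schedule.

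**The concern.** The SD visits in question were assessed and were not responses; visits with no usable assessment have their own bullet. In the sequence PR, SD, SD, PR, no two successive visits show a response, yet the subject counts as a confirmed responder. That is hard to square with a score that must last one cycle.

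The SAP is also stricter elsewhere. Its rule for CR allows only unknown or missing assessments between the two CRs. Its rule for the Prince criteria (SAP 6.4.3) requires three consecutive visits. Only PR under the primary criteria tolerates assessed non-responses.

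The bullet can add responders but never remove them, and the trial has a single success criterion. SAP 6.5.3.1 plans one sensitivity analysis of the response rate, by steroid use. The report would therefore not show how many responders depend on the SD allowance.

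**Working it through.** **1. The plan's own figure.** Exact Clopper-Pearson limits for x of n are the 2.5% quantile of Beta(x, n−x+1) and the 97.5% quantile of Beta(x+1, n−x). For 25/70 this gives 24.61% to 48.07%, which agrees with the 25% to 48% in SAP section 5 after rounding. Unrounded, 24.61% does not exceed 25%. The smallest passing count is 26/70 = 37.1%, with limits 25.89% to 49.52%. One subject therefore separates failure from success.

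**2. Does the 3-week condition restrict the SD bullet?** With scheduled 21-day visits and a 3-day early window, the shortest gap between the two responses is:
- one SD between: 2 × 21 − 3 = 39 days
- two SDs between: 3 × 21 − 3 = 60 days

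Both exceed 21 days, also after allowing for the 1-day leeway in cycle starts. The condition can matter only for adjacent visits.

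**3. The rules side by side.**

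| Sequence on 21-day visits | Score held from one visit to the next? | SAP 6.4.1 |
|---|---|---|
| PR, PR (at least 21 days apart) | yes | confirmed PR |
| PR, SD, PR | no | confirmed PR |
| PR, SD, SD, PR | no | confirmed PR |
| PR, then SD only | no | not a response |
| CR, SD, CR | no | not a CR |

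**4. Effect on the decision, without a disease model.** The documents give no frequency for the interrupted pattern. Suppose the true rate without the bullet is 25%, and a further fraction q of subjects count only through it. The chance of success is P(X ≥ 26), with X binomial (70, 0.25 + q):

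| q | extra responders (70 × q) | chance of success |
|---|---|---|
| 0 | 0 | 1.6% |
| 1% | 0.7 | 2.6% |
| 2% | 1.4 | 4.1% |
| 3% | 2.1 | 6.1% |
| 5% | 3.5 | 12.1% |

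**5. What q might be.** This step rests on assumptions. Each subject has a fixed true log ratio of mSWAT to baseline, normal with between-subject SD 0.4 to 0.8. Visit noise has SD 0.10 to 0.40. There are 7 on-treatment assessments, 8% drop-out per visit, and stopping at a 25% increase. PR is a ratio of 0.5 or less. The mean is set so that two consecutive PRs give 25%. The SAP rule is then applied to the same subjects, for three values of the lag-1 correlation of the visit noise:

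| Correlation | Mid case (SD 0.6, noise 0.20): rate; chance of success | Extra responders per 70, whole grid | Chance of success, whole grid |
|---|---|---|---|
| 0 | 27.6%; about 5% | about 0.7 to 4 | about 2.6% to 15–18% |
| 0.5 | about 26.2%; about 2.8% | 0.3 to 1.8 | 2.0% to 5.2% |
| 0.8 | 25.6%; about 2.1% | about 0.2 to 0.9 | 1.8% to about 3% |

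The result depends mainly on the visit noise and on the correlation between visits.

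**The case against.** The best defence is that SD after PR is not a loss of response in this protocol. The synopsis ends duration of response at PD, and Appendix 4 Table 2 defines loss in skin as a rise above nadir plus 50% of the baseline score. A subject who moves from 48% to 52% of baseline becomes SD without meeting either definition. Appendix 4, section 6 does not use the word consecutive, and the SAP still demands a second PR or CR.

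Part of this stands: two consecutive visits is a reading of the protocol, not its text. It does not rescue the bullet. The PD definitions say when an established response ends, whereas section 6 says whether there is one. If SD preserved a response, a single PR followed only by SD would also qualify, and the SAP does not accept that.

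Stronger readings are tempting, and the documents do not support them:
- **The rule doubles the false-positive rate.** A chance of success of about 5%, against the nominal one-sided 2.5%, needs independent noise between visits. The protocol prefers the same assessor throughout, so some correlation is likely; at 0.8 the mid case stays below 2.5%.
- **The bullet distorts duration of response because SD visits count inside it.** They count for every responder, since duration runs to PD or death. Adding fragile responders could even shorten the median.
- **The disease fluctuates from visit to visit.** The protocol's phrase, "cutaneous symptoms waxing and waning over a period of years", describes natural history, not 3-weekly change on treatment.
- **The change is hidden.** SAP 8.1 refers to the revision table, which lists the update of the response rules. The fair criticism is that the table calls it a clarification and does not name the SD allowance.
- **Any single PR now counts.** It does not; the PR must return.

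There are also partial safeguards: the IRC response rate under the Prince criteria and the swimmer plot of timepoint responses.

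**Conclusion.** The concern holds as an unreconciled confirmation rule in the primary endpoint, with no response rate planned without it. The direction is certain: upward or zero. The size is not known from the documents, and it is zero if no subject shows the pattern. Under the models above it is about 0.2 to 4 responders per 70, with a chance of success of about 1.8% to 15–18% against 1.6%. Those models treat skin only, assume a flat true course for each subject, and take two consecutive responses as the protocol's meaning. A reader might infer that the response rate needs to pass 25%. That threshold applies to the lower confidence limit, so the rate needed is 37.1% (26/70), and a single interrupted responder can decide the outcome there.

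**What to change.** In the primary and skin derivations (SAP 6.4.1 and 6.4.2), require two responses (PR or CR) at least 3 weeks apart with no assessed non-response between them. Leave unknown and missing visits to the existing bullet. Report the SD-tolerant rate as a named sensitivity analysis with its exact interval and the number of responders who depend on it. Record the rule in SAP 8.1 as a departure from Appendix 4, section 6. If the sponsor keeps the allowance in the primary analysis, the minimum is a stated rationale in 8.1 and the strict rate reported beside it.

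The cost is wording in the SAP and the ADaM specification, settled before database lock. No new data are needed, and the sample size and the 26/70 boundary do not change. The downside is that the reported response rate may be slightly lower.
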